1.0 PROTOCOL SUMMARY AND/OR SCHEMA

Title

Colesevelam for lenalidomide-associated diarrhea

Primary Objective

The primary objective is to evaluate the ability of colesevelam to improve lenalidomideassociated diarrhea in patients with multiple myeloma treated with lenalidomide maintenance.

Patient population

Patients with multiple myeloma, age 18 years or older, treated with maintenance lenalidomide. Patients who experience grade 1 or worse diarrhea on lenalidomide will be treated with colesevelam.

Study design

This is a single arm, phase II trial of colesevelam for lenalidomide-associated diarrhea. Up to 40% of myeloma patients on lenalidomide maintenance experience some degree of diarrhea. There is currently no established treatment standard for patients who develop diarrhea during lenalidomide and available anti-diarrheal (i.e. loperamide, opioids) may not give optimal symptom relief. In this trial we will assess whether colesevelam, a bile acid sequestrant, can improve diarrhea associated with lenalidomide maintenance therapy in patients with grade 1 or more diarrhea. The target will be that 30% of patients with lenalidomide-associated diarrhea will have an improvement by at least 1 grade or returns to patients baseline when receiving colesevelam. A total of 25 patients will accrue on the study in a Simon's two-stage minimax design. Patients will initially be started on 1250 mg (2 x 625 mg tablets) and the dose can be increased to maximum of 6 tablets per day based on efficacy and tolerability. Treatment will be continued until drug-related toxicity, worsening of diarrhea, or diarrhea that remains grade 1 or higher at week 2. Each patient will be followed for 12 weeks after colesevelam initiation.

Secondary objectives in the study include assessment of gastrointestinal (GI) symptoms the Patient Reported Outcomes within the Common Terminology Criteria for Adverse Events (PRO-CTCAE), as well as assessment of diet using a dietary questionnaire.

Lenalidomide pharmacokinetics will be assessed in up to 15 patients to assess possible drug interactions between lenalidomide and colesevelam. In these patients, a blood sample will be drawn pre- and 2 hours post the first colesevelam dose (day 1), as well as pre- and 2 hours post colesevelam on day 8 after initiation of colesevelam. Research stool samples will be collected at baseline and after 12 weeks of treatment for microbiota and bile acid studies.

Treatment Plan

Patients will be treated with colesevelam, starting dose 1250 mg (2 x 625 mg tablets) which can be increased to up to 6 tablets per day based on efficacy and tolerability. Response will be evaluated after 1, 2, 4, and 12 weeks after start of colesevelam. Patients will be treated with colesevelam on the study for up to 12 weeks.

2.0 OBJECTIVES AND SCIENTIFIC AIMS

Primary objective

To evaluate the ability of colesevelam to improve lenalidomide-associated diarrhea in patients with multiple myeloma treated with lenalidomide maintenance. Diarrhea will be evaluated using Common Terminology Criteria for Adverse Events (CTCAE) grading. The primary end-point is improvement of diarrhea by at least 1 grade or returns to patients baseline when receiving colesevelam according to CTCAE 5.0 scale by 4 weeks of treatment with colesevelam.

Secondary objective

- To assess GI symptoms using the Patient Reported Outcomes within the Common Terminology Criteria for Adverse Events (PRO-CTCAE)
- To assess diet before and while on treatment with colesevelam.
- To further describe diarrhea during the study period using the Bristol Stool Form Scale.3
- Describe duration of response by week 12 (end of study)

Correlative studies

- To assess lenalidomide pharmacokinetics while on colesevelam
- Collection of research stool samples for GI microbiota and bile acid assessment

3.0 BACKGROUND AND RATIONALE

Multiple Myeloma - Disease Overview

Multiple myeloma (MM) is a malignant plasma cell disorder characterized by hypercalcemia, anemia, renal insufficiency, lytic bone disease, or other myeloma-related events (serum free chain ratio ≥100, >1 focal lesions on PET-CT or magnetic resonance imaging, or >60% clonal plasma cells in the bone marrow). Multiple myeloma accounts for 1% of all cancers and 10-15% of all hematological malignancies. Median age at diagnosis is 69 years. According to data from the Surveillance, Epidemiology, and End Results program, 30,770 new myeloma cases are estimated to be diagnosed in 2018 in the US.

Myeloma is treated with induction therapy where the standard in young and fit patients is a combination of three drugs with different mechanisms of action. The most common three-drug combinations are carfilzomib/lenalidomide/dexamethasone or bortezomib/lenalidomide/dexamethasone. Induction therapy is followed by consolidation therapy which may include high-dose melphalan chemotherapy with autologous stem cell transplantation. Induction and consolidation treatment is in the majority of patients followed by maintenance therapy with lenalidomide.

Lenalidomide and Multiple Myeloma

Lenalidomide (Revlimid®) is an immunomodulatory (IMiD) compound with anti-neoplastic activity that stems from several potential mechanisms of action, including direct induction of apoptosis, inhibition of angiogenesis, and inhibition of pro-survival signals to tumor cells and stimulation of host anti-tumor immunity. Lenalidomide is FDA approved for maintenance in multiple myeloma.⁴ According to several clinical trials and a recent meta-analysis, lenalidomide maintenance prolongs progression-free survival and overall survival.^{2,5-8}

Lenalidomide-associated diarrhea

Although lenalidomide is well tolerated in the majority of patients, possible side effects include pancytopenia, rash, and GI toxicities including diarrhea.^{2,6} Lenalidomide-associated diarrhea can impact patient's quality of life and may lead to unnecessary dose reductions and discontinuation of therapy which can potentially compromise the disease outcome. Therefore, optimal management of the diarrhea is essential. In practice, loperamide and opioids have been used to treat lenalidomide-associated diarrhea, however, the clinical experience is that the effect of these medications is often suboptimal.

The incidence of lenalidomide-associated diarrhea, any grade, has been documented to occur in up to 25-40% of patients in treated with lenalidomide +/- dexamethasone in clinical trials (approximately 2-3% being grade 3 or 4 diarrhea). 1,2,9 In a recent meta-analysis including three major randomized controlled trials on lenalidomide maintenance, 2-3% of patients discontinued treatment due to diarrhea. There is currently limited information on outcomes in patients who discontinue lenalidomide maintenance due to diarrhea in comparison to those who continue. However, progression free survival and overall survival was longer in patients on lenalidomide maintenance versus those not on maintenance in a recent metaanalysis.8

In a recent a case series, 12 patients with lenalidomide-associated diarrhea were assessed to better understand underlying mechanisms of the diarrhea. All patients underwent work up to exclude GI infections, lactose intolerance, celiac disease, inflammatory bowel disease, neoplasia, bacterial overgrowth, pancreatic insufficiency, and bile acid malabsorption. Selenium homocholic acid taurine (SeHCAT) scanning revealed severe bile acid malabsorption in 9 patients and mild bile acid malabsorption in 1 the 12 patients. Thus, bile acid malabsorption was suggested as an underlying cause for lenalidomide-associated diarrhea.

Investigational drug colesevelam

Cholesterol is the major precursor of bile acid. Colesevelam (Welchol®) is a bile acid sequestrant which binds with bile acids in the intestine to form an insoluble complex that is eliminated in feces. The increased excretion of bile acids results in an increased oxidation of cholesterol to bile acid and a lowering of the serum cholesterol. Therefore, colesevelam has been FDA approved for lowering low-density lipoprotein (LDL) cholesterol and HbA1c in patients with primary hyperlipidemia and/or type 2 diabetes mellitus.

There is increasing data on the use of colesevelam in patients with diarrhea due to bile acid malabsorption in the setting of Crohn's disease and irritable bowel syndrome. 11,12 There are also anecdotal reports that suggest that patients with lenalidomide-associated diarrhea might benefit from dietary modifications and/or colesevelam. 10 In the above mentioned case series of 12 patients with GI symptoms (including diarrhea, urgency, fecal incontinence, and abdominal cramps) after starting lenalidomide; all patients were treated with low-fat diet and/or colesevelam. Two patients had improved symptoms on low-fat diet only. The remaining 10 patients were treated with colesevelam (+/- low-fat diet) in doses up to 6 tablets of 625 mg per day, split into doses with food and > 4 hours before or after lenalidomide administration. Of these 10 patients, 5 had normalization of bowel habits; the other 5 had improved symptoms with reductions in stool frequency and/or improvement in stool consistency.¹⁰ In the case series of 12 patients, however, there is no information on severity (i.e. grade) of diarrhea, neither at baseline nor after intervention. The authors conclude that bile acid malabsorption is a major cause of lenalidomide-associated diarrhea and can be improved by using bile acid sequestrants such as colesevelam. 10 Confirmatory clinical trials are warranted to confirm the benefit of a bile acid sequestrant in lenalidomide-associated diarrhea.

4.0 OVERVIEW OF STUDY DESIGN/INTERVENTION

4.1 Design

This is a single institution, single arm, open label phase II trial to evaluate the efficacy of colesevelam for myeloma patients on lenalidomide maintenance who experience grade 1 or more diarrhea. Patients will be given colesevelam at a starting dose of 2 tablets (2 x 625 mg) which can be increased to up to 6 tablets per day depending on efficacy and tolerability, see dose adjustment schedule section 9.2, page 16. Patients can continue on the study until unacceptable toxicity, diarrhea that remains grade 1 or higher at week 4, worsening of diarrhea at any point, or end of study (12 weeks), whichever comes first. Each patient will be followed for a total 12 weeks.

The primary endpoint of this study is improvement of diarrhea. Response is defined as improvement by at least 1 grade according to CTCAE version 5.0 (see page 15) or returns to patients baseline when receiving colesevelam. A total of 25 patients will accrue on the study in a Simon's two-stage minimax design. In the first stage of the study, 16 patients will accrue. If 1 or fewer patients have a reduction in diarrhea severity, the study will stop due to a lack of efficacy; otherwise, an additional 9 patients will accrue. We estimate that the accrual to the study will be approximately two patients per month. The study is expected to be completed in approximately two years.

A diarrhea diary will be filled out by patients to capture frequency and consistency of bowel movements. GI symptoms will be assessed using the GI oriented PRO-CTCAE questions. Diet will be recorded at several time points to assess changes in dietary intake prior to and while on colesevelam. Stool consistency will be assessed using the Bristol Stool Form Scale. Correlative studies include pharmacokinetic (PK) evaluation of lenalidomide as well as collection of stool for studies of the GI microbiome.

4.2 Intervention

All patients should be on maintenance single agent lenalidomide and experiencing grade 1 or higher diarrhea according to the CTCAE grading system. For treatment with colesevelam, the starting dose will be 1250 mg (2 x 625 mg) with food which can be increased to 6 tablets max per day based on efficacy and tolerability. Coleveselam should not be taken within 4 hours before or after lenalidomide and other interacting medications. All participants will be given a pill diary to record intake of colesevelam (Appendix 1). The effect of colesevelam on lenalidomide-associated diarrhea will be evaluated after 1, 2, 4, 12 weeks after start of treatment. If the diarrhea does not respond to the starting dose of colesevelam, the dose can be increased every 2 days to 2 tablets two times per day (2 x 625 mg BID) and later to 3 tablets two times per day (3 x 625 mg BID). The colesevelam dose can be decrease to 1 tablet per day if there has been improvement of diarrhea but emergence of side effects. Treatment with colesevelam will continue until drug-related toxicity, diarrhea that remains grade 1 or higher at week 2 despite dose elevations, or if worsening diarrhea occurs, or up to 12 weeks on study.

Patients will be evaluated by their physician and/or research nurse at baseline, after 1 week (+/- 2 days), after 2 weeks (+/- 2 days), after 4 weeks (+/- 7 days), and 12 weeks (+/- 7 days) for efficacy, toxicity, and compliance. The evaluations after 1, 2, and 4 weeks will preferably as office visits but can be replaced by telephone calls for sake of convenience.

Pharmacokinetics will be assessed in a subset of patients (up to 15 patients) at baseline and 8 days after start of colesevelam. All patients will be asked to participate in the PK studies and the first 15 who consent to this correlative part will be included. Research stool samples will be collected for all study participants at baseline and after 12 weeks of study.

Patients that repond to colesevelam can continue on the drug after the 12 weeks of study treatment. Coverage for colesevelam costs after the 12 weeks will not be covered by the trial but will go through patient's insurance.

5.0 THERAPEUTIC/DIAGNOSTIC AGENTS

This study is IND exempt.

5.2 Colesevelam (Welchol®)

Welchol® (colesevelam hydrochloride) is a non-absorbed, polymeric, lipid-lowering and glucose-lowering agent intended for oral administration. Colesevelam hydrochloride is a high-capacity bile acid-binding molecule.

Colesevelam hydrochloride is poly (allylamine hydrochloride) cross-linked with epichlorohydrin and alkylated with 1-bromodecane and (6-bromohexyl)-trimethylammonium bromide. The chemical name (IUPAC) of colesevelam hydrochloride is allylamine polymer with 1-chloro-2, 3-epoxypropane, [6- (allylamino)-hexyl]trimethylammonium chloride and N-allyldecylamine, hydrochloride. The chemical structure of colesevelam hydrochloride is represented in the figure below.

Figure 1. Colesevelam chemical structure

Indications and Usage

Colesevelam is FDA approved for the indication of lowering LDL cholesterol and HbA1c in patients with primary hyperlipidemia and/or type 2 diabetes mellitus. Due to the bile acid binding effect, colesevelam has also been used for treatment of bile acid malabsorption in irritable bowel syndrome and inflammatory bowel disease.

Adverse Events

The most common adverse events during treatment with colesevelam include GI symptoms mainly constipation, dyspepsia, and nausea.¹³ Hypoglycemia was observed in up to 3% of patients with diabetes mellitus. Several drug interactions were also observed, primarily with medication with a narrow therapeutic interval including oral anticoagulants and anticonvulsive drugs (see section 3.0, page 8).

Table 1. Potential adverse events with colesevelam

COMMON, SOME MAY BE SERIOUS

In 100 people receiving Colesevelam, more than 4 and up to 100 may have:

- Constipation
- Dyspepsia (indigestion)
- Nausea
- Hypertension
- Back Pain
- Abdominal Pain
- Infection
- Headache

RARE. AND SERIOUS

In 100 people receiving Colesevelam, 3 or fewer may have:

 Hypoglycemia (low blood sugar – symptoms include confusion, heart palpitations and shakiness)

Formulation

The Welchol tablet is an off-white, oval, film-coated, solid tablet containing 625 mg colesevelam hydrochloride. In addition, each tablet contains the following inactive ingredients: magnesium stearate, microcrystalline cellulose, silicon dioxide, HPMC (hydroxypropyl methylcellulose), and acetylated monoglyceride. The tablets are imprinted using water-soluble black ink.

Mechanism of Action

Colesevelam hydrochloride, the active pharmaceutical ingredient in Welchol®, is a non-absorbed, lipid-lowering polymer that binds bile acids in the intestine, impeding their reabsorption.

Storage

Store at 25°C (77°F); excursions permitted to 15°C to 30°C (59°F to 86°F). Protect from moisture.

Pharmacokinetics and Drug Metabolism

Colesevelam hydrochloride is a hydrophilic, water-insoluble polymer that is not hydrolyzed by digestive enzymes and is not absorbed. It is not metabolized systemically and does not interfere with systemic drug-metabolizing enzymes such as cytochrome P-450. In 16 healthy volunteers, an average of 0.05% of administered radioactivity from a single ¹⁴C-labeled colesevelam hydrochloride dose was excreted in the urine.

Prescribing Information

Welchol (colesevelam) will be provided free of charge from Daiichi Sankyo, Inc. to the research subjects for 12 weeks durations only.

Administration

Patients should be advised to take Welchol® tablets with a meal and liquid. It can be taken to a maximum of 6 tablets once daily or 3 tablets twice daily.

Interactions

Colesevelam interacts with a number of drugs. Drugs with known interactions with colesevelam (cyclosporine, glimepiride, glipizide, glyburide, levothyroxine, olmesartan medoxomil, oral contraceptives [ethinyl estradiol, norethindrone], and metformin extended release) should be administered at least 4 hours prior to, or after colesevelam. Clinical trials and postmarketing reports in patients treated with colesevelam to reduce serum cholesterol include:

- Increased incidence of hypoglycemia in patients with diabetes mellitus
- Increased seizure activity or decreased phenytoin levels in patients receiving phenytoin. Administer phenytoin 4 hours prior to colesevelam.
- Reduced International Normalized Ratio (INR) in patients receiving warfarin. Monitor INR.
- Elevated thyroid-stimulating hormone (TSH) in patients receiving thyroid hormone replacement therapy. Administer thyroid hormones 4 hours prior to colesevelam.

Drugs that have not been tested for interaction with colesevelam, especially those with a narrow therapeutic index, should also be administered at least 4 hours prior to Welchol. Therefore in the published case-series, the investigators chose to separate lenalidomide administration from colesevelam administration by 4 hours. However, there is no information on potential effects of colesevelam on the absorption and pharmacokinetics of lenalidomide.

6.0 CRITERIA FOR SUBJECT ELIGIBILITY

6.1 Subject Inclusion Criteria

Patients must meet all the following criteria to be eligible for treatment on study:

- Memorial Sloan Kettering Cancer Center (MSK) confirmed diagnosis of multiple myeloma
- Treatment with single agent lenalidomide maintenance
- Patient must be ≥18 years of age at the time of informed consent
- Experiencing grade 1 or more diarrhea according to the CTCAE 5.0 criteria for at least 4 out of 7 days preceding screening and study inclusion.
- Scheduled to receive lenalidomide maintenance cycles at MSK
- Willingness and ability to comply with scheduled visits, treatment plan, laboratory tests and other study procedures

6.2 Subject Exclusion Criteria

- Patients with history of bowel obstruction
- Patients with serum triglyceride levels >300 mg/dL
- Patient with history of hypertriglyceridemia-induced pancreatitis
- Patients with known hypersensitivity to colesevelam or any component to the formulation
- Patients currently already receiving a bile acid sequestrant or have previously used bile acid sequestrant drugs for diarrhea and had no benefit
- Patients with diarrhea secondary to infection. Stool studies for GI pathogens should be collected prior to starting colesevelam but do not need to be resulted prior to starting Day 1 dose of colesevelam, unless infection is suspsected by the treating investigator, in which case Clostridium difficile PCR when clinically indicated, GI pathogen panel, stool ova and parasites, Giardia and Cryptosporum stool antigen tests will need to be resulted at investigator discretion.

7.0 RECRUITMENT PLAN

This study will be conducted at MSK. Efforts will be made to ensure that women and minority groups are adequately represented in this trial. All patients will be seen by MSK myeloma physicians and associated MSK co-investigators, enrolled and registered at MSK. All co-investigators agree to follow the treatment protocol and to conduct the proposed investigation according to recognized principles of good clinical practice. Participation is voluntary. Patients who report diarrhea while on lenalidomide maintenance will be approached and informed about the study by their physician. The Myeloma Service research nurses will then discuss the study details with patients and screen patients for eligibility. Every patient will be informed of the procedures to be followed, the potential benefits, side effects, risks, and discomforts of the trial and of potential therapeutic alternatives. All participants will be

required to sign statements of informed consent and research authorization that conform to FDA, IRB and HIPPA guidelines. Informed consent will be documented by the use of a written consent form approved by the MSK IRB.

8.0 PRETREATMENT EVALUATION

Evaluation of Inclusion and Exclusion criteria

The pretreatment evaluation can be done either during screening or up to 14 days before start of treatment on study or at baseline. In the event that the samples (stool studies to exclude GI pathogens and serum triglycerides) are taken at baseline, the patient can start study drug and will be taken off study if failure to fulfill inclusion criteria.

Grading of diarrhea as an adverse event is graded according to CTCAE version 5.0. To be eligible on the study, patients need to have grade 1 or more diarrhea according to the CTCAE definition. The CTCAE definition can be found at the National Institutes of Health website. https://ctep.cancer.gov/protocolDevelopment/electronic applications/ctc.htm

Table 2. Diarrhea grading according to CTCAE version 5.0

Grade	Description			
Grade 0	No diarrhea present			
Grade 1	Increase of <4 stools per day over baseline, mild increase in ostomy output compared to baseline			
Grade 2	Increase of 4-6 stools per day over baseline, moderate increase in ostomy output compared to baseline; limiting instrumental ADL			
Grade 3	Increase of ≥7 stools per day over baseline; hospitalization indicated; severe increase in ostomy output compared to baseline; limiting self care ADL			
Grade 4	Life-threatening consequences; urgent intervention indicated			

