8.2 Laboratory assessment

The following studies and laboratory tests will be completed within 0-14 days prior to colesevelam treatment:

- Complete blood count with differential count
- Comprehensive metabolic panel: sodium, potassium, chloride, carbon dioxide, serum creatinine, glucose, blood urea nitrogen (BUN), EGFR, albumin, calcium, magnesium, phosphorus, alkaline phosphatase, ALT, AST, total bilirubin, direct bilirubin, uric acid, LDH, total protein
- Serum protein electrophoresis (SPEP) and serum immunofixation to assess for presence and quantity of monoclonal protein (M-protein)
- Serum free light chain studies
- Quantitative immunoglobulins
- Serum triglycerides

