10.2 Laboratory assessment

Laboratory assessment will include:

- Complete blood count with differential count
- Comprehensive metabolic panel: sodium, potassium, chloride, carbon dioxide, serum creatinine, glucose, blood urea nitrogen (BUN), EGFR, albumin, calcium, magnesium, phosphorus, alkaline phosphatase, ALT, AST, total bilirubin, direct bilirubin, uric acid, LDH, total protein
- Serum protein electrophoresis (SPEP) and serum immunofixation to assess for presence and quantity of monoclonal protein (M-protein)
- Serum free light chain studies
- Quantitative immunoglobulins

Hematology and chemistry panels will be performed during screening, at 4 weeks (+/-7 days), and at the end of trial (12 weeks +/-7 days).

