10.4 Diarrhea assessments (primary endpoint)

Diarrhea assessments using the CTCAE scale will be performed at baseline (day 1 of colesevelam), at 1 week (+/- 2 days), 2 weeks (+/- 2 days), 4 weeks (+/- 7 days), and at 12

weeks (+/- 7 days). The assessment on week 1, 2, and 4 can be carried out as a telephone call by the treating physician or research nurse for reasons of convenience. In this event, the information regarding response will be collected over the phone and questionnaires will be handed in or sent to MSK.

Frequency and consistency of diarrhea/bowel movements will be recorded using a diarrhea questionnaire (Appendix 2). This will be used to grade the diarrhea according to the CTCAE scale (CTCAE, see section 8.0, page 15).¹⁴

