10.10 Table 4. Overview of time points for sampling and clinical assessment

	Baseline	Cycle 1 Day 1 (Within 14 days of baseline)	Cycle 1 Day 8 (+/-7 days)	Cycle 1 Day 15 (+/-7 days)	4 weeks/ End of Cycle 1 (+/- 14 days)	12 weeks / End of Cycle 3 (+/- 21 days)
MD/RN assessment	Visit		Visit or telephone assessment	Visit or telephone assessment	Visit or telephone assessment	Visit
Stool studies GI pathogens ^a	Xa					
Triglycerides	X					
CBC	X					X
Comp	X					X
SPEP, IFE and FLC	X					X
Stool Diary (response assessment) and Bristol Stool Scale ^b	Х		X	х	Х	Х
PRO-CTCAE	X		X	Х	Х	Х
Nutritional Survey ^c						Х
PK studies ^d		Χq	Xq			
Research stool samples ^e	Х					X

- a. Stool studies for GI pathogens should be collected prior to starting colesevelam but do not need to be resulted prior to starting Day 1 dose of colesevelam, unless infection is suspsected by the treating investigator.
- b. Response assessments (Stool diaries) will be done at Cycle 1 Day 8, Cycle 1 Day 15, end of Cycle 1 (week 4) and end of Cycle 3 (week 12). If diarrhea does not improve by at least 1 grade from baseline (using CTCAE version 5.0) or to patient's baseline bowel pattern by the end of Cycle 1 they will be removed from study.
- c. Patients will complete one nutrtional survey ("Food and Activitity Questionaire" survey will be used) and return at week 12 visit.

- d. Lenalidomide pharmacokinetics will be assessed in up to 15 patients to assess possible drug interactions between lenalidomide and colesevelam. In these patients, a blood sample will be drawn pre- and 2 hours post the first colesevelam dose (day 1), as well as pre- and 2 hours post colesevelam on day 8 after initiation of colesevelam.
- e. Research stool samples will be collected at baseline and after 12 weeks of treatment for microbiota and bile acid studies.

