11.0 TOXICITIES/SIDE EFFECTS

Colesevelam (Welchol®) is provided to investigator by Daiichi Sankyo, Inc.

In clinical trials, the most common side effects with colesevelam (incidence \geq 2% greater than placebo) include constipation, dyspepsia, and nausea. In trials including patients with diabetes, the overall incidence of hypoglycemia was 3.0% in colesevelam-treated patients and 2.3% in placebo-treated patients.

Postmarketing reports with concomitant colesevelam administration include drug interactions with phenytoin, warfarin, and thyroid hormone replacement therapy (section 3.0, page 9). These medications should be administered >4 hours prior or after colesevelam and the serum concentration and therapeutic effect should be monitored. Other postmarketing reports include bowel obstruction, dysphagia, esophageal obstruction, fecal impaction, hypertriglyceridemia, pancreatitis, and increased transaminases.

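### Section 8.0 allows the first colesevelam dose before a baseline triglyceride result is known, while Section 6.2 excludes values above 300 mg/dL and allows pending results for stool studies only (minor, cheap to fix)

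*Combined protocol and SAP*

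**What the plan says.** Section 6.2 lists as an exclusion "Patients with serum triglyceride levels >300 mg/dL", with no qualification about timing. The same section lets stool pathogen results be outstanding at the first dose, "unless infection is suspsected by the treating investigator". Note a to Table 4 (Section 10.10) repeats this for the stool row: "Stool studies for GI pathogens should be collected prior to starting colesevelam but do not need to be resulted". The triglyceride row of Table 4 carries no such note.

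Section 8.0 names both the stool studies and serum triglycerides. If these samples are taken at baseline, "the patient can start study drug and will be taken off study if failure to fulfill inclusion criteria".

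Section 8.2 includes serum triglycerides among the tests that "will be completed within 0-14 days prior to colesevelam treatment". Section 15.1 asks for eligibility to be confirmed against the inclusion and exclusion criteria as part of registration.

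**The concern.** The triglyceride limit reads as a safety criterion. Section 11.0 says of colesevelam: "Other postmarketing reports include bowel obstruction, dysphagia, esophageal obstruction, fecal impaction, hypertriglyceridemia, pancreatitis, and increased transaminases". Section 6.2 also excludes, separately, a history of pancreatitis caused by high triglycerides. An exclusion of this kind protects the patient only if its result is read before dosing.

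Under Section 8.0 the result may be read afterwards. A patient above 300 mg/dL could then take study drug until the value returns and someone acts on it. Staff working from Section 6.2 or Table 4 would find no such permission for triglycerides. Staff working from Section 8.0 would find it stated outright, so two sites of instruction could lead to different handling of the same patient.

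The sentence has two smaller faults. Read alone, it would let a patient with suspected infection start before stool results are back, because the condition in Section 6.2 is not carried over. It also ties removal to inclusion criteria, although high triglycerides and infectious diarrhea are both exclusions.

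**Working it through.** The point is a comparison of texts, and the plan states no figure to reproduce.

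1. **Which results may be pending.** Section 6.2: stool studies, with a condition. Table 4 note a: stool studies, with the same condition. Section 8.0: stool studies and triglycerides, with no condition. Triglycerides appear in one of the three places, and the infection condition in two.

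2. **What Section 8.0 permits.** It does not use the word pending. But starting drug and then removing a patient who fails the criteria makes sense only if the result was unknown at the first dose.

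3. **Whether the case can arise.** Section 8.2 accepts a draw 0 days before treatment. Section 10.4 equates baseline with day 1 of colesevelam, although it does so for diarrhea grading, and Table 4 keeps Baseline and Cycle 1 Day 1 in separate columns. A day-of-dosing draw is therefore allowed but not required. Samples taken earlier in the 14 days will often be resulted in time.

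4. **What exposure could follow.** The starting dose is 2 tablets daily. Section 9.2 allows an increase after 2 days on each level: to 2 tablets twice daily after 2 days, and to 3 tablets twice daily after 2 + 2 = 4 days. A result that is late or overlooked could therefore arrive after escalation to the maximum of 6 tablets a day. A result returned promptly would limit exposure to the starting dose.

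5. **How many patients.** The expected number would be 25 × (share drawn on the day of dosing) × (share of those not resulted before the dose) × (share of those above 300 mg/dL). The documents give none of the three shares, nor any laboratory turnaround time. Any figure would only restate the values assumed for them, so none is offered.

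**The case against.** The strongest reply is that Section 8.0 is a deliberate rule. Section 6.2 sets a limit without saying when the result is due; Section 8.0 supplies the timing, names triglycerides and states the consequence. Section 8.2 is satisfied by a day-0 draw, and Section 15.1 is general registration text that does not mention laboratory results. On this view the sections can be read together. That much stands, and a reader who inferred that the protocol flatly contradicts itself would go too far. It still leaves a pending-result allowance written for stool studies in two places and widened in a third, with no reason given for the widening.

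Second, some protection exists. A history of pancreatitis from high triglycerides can be checked before dosing, the starting dose is low, and a failing result leads to removal. This also stands and limits the weight of the point. It does not cover a patient above the limit who has no such history.

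Third, a reader might point to the absence of any later triglyceride test. Section 10.2 says "Hematology and chemistry panels will be performed during screening, at 4 weeks (+/-7 days), and at the end of trial", triglycerides are not in its list, and Table 4 marks them at baseline only. That is true, but on-treatment monitoring is a separate question. The single test exists whether it is read before or after the first dose, and the change proposed here adds no repeat.

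Fourth, waiting for the result may have a practical cost. Up to 15 patients have pharmacokinetic blood drawn before and 2 hours after the first colesevelam dose (Sections 8.6 and 10.6). If dosing waits for a same-day triglyceride result, those draws move as well, possibly to another attendance. This is fair and is counted in the cost below.

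**Conclusion.** The point holds as a minor one. Followed as written, Section 8.0 can lead to a patient being dosed against a safety exclusion, and its wording does not match Section 6.2 or Table 4 note a. Closing the gap brings a modest gain in patient safety, which the documents do not allow to be quantified. They say nothing about the harm of a brief exposure at the starting dose. The conclusion assumes that the 300 mg/dL limit is there for safety, which Sections 6.2 and 11.0 suggest but do not state.

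Two stronger readings are not supported. A reader might infer that the efficacy result is biased; nothing in the documents links high triglycerides to diarrhea response. A reader might also infer that patients later found to have had an infection would stay in the 25 and count as successes. Section 14.0 replaces patients removed before the 1-week evaluation for reasons other than worsening or drug toxicity, and it does not say how a later removal for ineligibility is classified. Retention as a success is therefore conjecture. It would also need an unsuspected infection, a result acted on only after week 1, and a response already recorded. No change to Section 14.0 is sought on this ground, and the two-stage design is not in question.

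**What to change.** Replace the Section 8.0 sentence with:

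> Serum triglycerides must be resulted at 300 mg/dL or less before the first dose. Stool studies for GI pathogens must be collected before the first dose but need not be resulted unless the treating investigator suspects infection (Section 6.2). A patient found not to meet the inclusion or exclusion criteria will be taken off study.

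This corrects the triglyceride timing, restores the infection condition and covers both sets of criteria. Adding triglycerides to the allowance in Section 6.2 and Table 4 would also make the sections agree, but it would keep the exposure; if the sponsor wants that, the reason should be stated.

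The cost is wording, plus a short delay of the first dose, and of the day-1 pharmacokinetic draws where they apply, for patients whose triglycerides are drawn on the day of dosing. Drawing the sample earlier within the 14 days already allowed avoids the delay. No test is added.
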